Efficacy Criteria: Sensitivity and Specificity will be calculated separately for BIOZEK COVID-19 Antigen Rapid Test - on a self-collected, nasopharyngeal sample and for BIOZEK COVID-19 Antigen Rapid Test on the self-collected oral fluid sample.

Additionally, the result of each test performed by the subject will be compared to the RT-PCR test result.

End Points:

Sensitivity and Specificity of BIOZEK COVID-19 Antigen Rapid Test on self-collected nasopharyngeal sample.

Sensitivity and Specificity of BIOZEK COVID-19 Antigen Rapid Test on self-collected oral fluid sample.

Table of Contents

1. Protocol Synopsis	2
2. Introduction	6
3. Background	6
4. Study Objectives:	7
5. Investigational Product	7
6. Study Population	14
6.1 Inclusion Criteria	14
6.2 Exclusion Criteria	14
6.3 Sample Size	14
6.4 Confirmation of Patient Enrollment	14
6.5 Patient Identification	14
6.6 Removal, Replacement, or Early Withdrawals of Subjects	15
7. Overview of Investigational Plan and Study Administration	15
7.1 Enrollment	15
7.2 Material and Methods	15
7.3 Premature Discontinuation	16
7.4 Protocol Violations	16
7.5 Compliance	16
8. Data analysis.	17
9. Ethics	17
9.1 Hospital Ethics Committee/Institutional Review Board	17
9.2 Ethical Conduct of the Study	17
9.3 Subject Information and Consent	17
10. References	18

2. Introduction

Widespread testing is the cornerstone of COVID-19 control around the world. However, U.S. testing to identify people with infected SARS-CoV-2 has been slow to start and continues to lag. An important feature of SARS-CoV-2 is that it can be transmitted while a host is unaware of infection (asymptomatic). Epidemiologic evidence has demonstrated that pre-symptomatic and asymptomatic transmission of virus has driven the current epidemic¹. Antigen tests have a great potential for screening asymptomatic people². To limit outbreaks, testing is needed to identify as many individuals who are transmitting infection as quickly as possible. Antigen Tests have the potential to readily identify an individual who is at or near peak infection. Rapid Tests, while less sensitive, perform best during the early stages of COVID-19 infection; when viral load and potential for spread is high.

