There is an unmet need to provide broad testing that can serve high risk and low resource communities. The FDA's authorization for antigen tests for home use is helping to expand Americans' access to testing, reducing the burden on laboratories and test supplies³. The Biozek Antigen Rapid Test can be easily performed by untrained personnel with results in less than 15 minutes. The increased potential for repeated testing, remote or at home testing, could help contain the COVID-19 pandemic.

3. Background

In December 2019, an outbreak emerged identifying a novel coronavirus, severe acute respiratory syndrome coronavirus 2 (SARS-CoV-2). The World Health Organization (WHO) declared it a global pandemic in March 2020. Testing in the U.S. appeared to be insufficient for optimal early containment of the virus. With the resurgence of the disease (COVID-19), the U.S. has recently seen the highest number of hospitalizations since the beginning of the pandemic and rates are expected to increase in future weeks⁴. Given the continued community transmission of SARS-CoV-2 in the US, there has been sustained focus on the role of testing to reduce the spread. Presently, the gold standard polymerase chain reaction (PCR) test is used to diagnose COVID-19 by detecting the presence of specific genetic material of the virus. PCR test requires laboratory processing and it may take days to obtain results. In turn, an individual could be negative at time of testing but positive by the time the result is returned⁵. PCR testing is performed by a trained healthcare professional at an approved testing facility. In contrast, The BIOZEK Rapid Antigen Test detects specific proteins on the surface of the virus and it can be self-administered. Results are generated in 15 minutes and can be performed at home or any remote location. In efforts to meet the exponential demand in testing, the introduction of a new and effective Rapid Test could potentially end the spread of COVID-19.

4. Study Objectives:

To assess sensitivity and specificity of BIOZEK COVID-19 Antigen Rapid Test on a self-collected sample and self-performed test by subject (nasopharyngeal swab and oral fluid).

To assess subject's performance to collect samples and conduct BIOZEK COVID-19 Antigen Rapid Test.

5. Investigational Product

[figure not shown]

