1. Insert a sterile swab less than one inch (about 2 cm) into a nostril (until resistance is met at the turbinate).
2. Rotate the swab 5-10 times against the nasal wall. Using the same swab repeat the collection procedure with the second nostril.
3. Withdraw the sterile swab, avoid excess volume and high-viscous nasal discharge.

[figure not shown]

Caution: If the swab stick breaks during specimen collection, repeat specimen collection with a new swab.

Specimen Extraction –Nasopharyngeal Swab

Only the extraction buffer provided in this kit is to be used for specimen extraction.

1. Peel off the sealing on the extraction tube with extraction buffer inside.
2. Place the swab specimen into the extraction buffer, for better mixture and extraction to release the antigen, rotate the swab for approximately 10 seconds while pressing the swab head against the inner wall of the tube at least 5 times to release the antigen.
3. Remove the swab while squeezing the swab head against the inner wall of the tube to get maximum solution left inside the extraction tube. Dispose of the used swab in your biohazard waste.
4. Fit the tip onto the top of the extraction tube. Use extracted sample solution as final sample for testing as soon as possible.

NOTE: The storage of the extracted specimen is stable for 2 hours at room temperature or 24 hours at 2-8°C.

[figure not shown]
Testing Procedure – Nasopharyngeal Swab

Allow the test cassette, extracted sample solution and/or controls to equilibrate to room temperature (15-30°C) prior to testing.

1. Remove the test cassette from the sealed foil pouch and use it within one hour. Best results will be obtained if the test is performed immediately after opening the foil pouch.
2. Shake the extracted sample solution to mix it well. Invert the sample extraction tube and add 3 drops of the Extracted Sample Solution (approx.75-100µL) to the specimen well(S) of the

cassette. Start the timer.

3. Wait for the red line(s) to appear and read the result at 15 minutes. Do not interpret the result after 20 minutes.

[figure not shown]

Interpretation of results - Nasopharyngeal Swab

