POSITIVE: * Two red lines appear. One red line should be in the control region (C) and another red line should be in the test region (T). Positive result in the test region indicates detection of COVID-19 antigens in the sample. *NOTE: Red color line intensity in the test region (T) will vary based on the amount of COVID-19 antigen present in the sample. Any shade of red color in the test region (T) should be considered positive.

[figure not shown]
NEGATIVE: One red line appears in the control region (C). No apparent red line appears in the test region (T) indicates a negative COVID-19 antigen test result.

INVALID: No red line appears in the control region (C). Insufficient specimen volume or incorrect procedural techniques are the most likely reasons for control line failure. Review the procedures and repeat the test with a new cassette. If the problem persists, discontinue using the test kit immediately and contact your local BIOZEK products distributor.

Specimen Collection - Oral Fluid

[figure not shown]
Content

Advise the patient not to consume food, beverages, chewing gum, tobacco, and other substances at least 10 minutes prior to specimen collection.

Step 1

Connect the plastic tube (number 2) to the mouthpiece (number 1). Press the plastic tube as far as possible into the mouthpiece.

Step 2

If you are having trouble collecting saliva in your mouth, try closing your mouth and wiggling your tongue. Gently rubbing the outside of your cheeks, just behind your back teeth. Making chewing motions with your mouth.

NOTE: We recommend carrying out this step in the morning.

Step 3

Spit the oral fluid into the mouthpiece. There should be about 0.5 ml of liquid in the plastic tube. This corresponds to the bottom line on the plastic tube.

[figure not shown]

Step 4a

Remove the mouthpiece (number 1) and dispose of it in the specimen bag (number 8). Place the plastic tube in the holder (number 6).

Step 4b (only follow this step if there is too much saliva)

[figure not shown]
More than 0.5 ml of liquid? Take the pipette (number 3). Press and hold the bulb until the pipette protrudes into the solution of the plastic tube (1). Release the balloon slowly, so that the pipette sucks up the solution (2). Bring the liquid level to the bottom line (0.5 ml).

Specimen Extraction – Oral Fluid

Step 5

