Take the buffer (number 4) and remove the seal at the top (by cutting/breaking it). Squeeze the contents of the buffer into the plastic tube (number 2) containing the mucus/spittle.

[figure not shown]

Step 6

Put the cap (number 5) on the plastic tube (number 2).

Step 7

[figure not shown]
Knead the bottom of the plastic tube firmly (number 2) for 10 seconds to mix the buffer well with the mucus/spit.

Testing Procedure – Oral Fluid

Step 8

Tear open the test package and remove the test cassette. Turn the plastic tube (number 2) upside down and let 2 drops of liquid fall into the opening next to the letter S on the cassette (number 7).

[figure not shown]

Step 9

Wait 15 minutes.

Step 10

Read the result Positive: You have tested positive for COVID-19 antigens, so please contact your doctor. Negative: You have tested negative, so the test did not detect any antigens in your sample. However, if you have COVID-19 related complaints, please contact your doctor. Invalid: The test cannot be displayed, so contact your supplier for further instruction. Do not throw the test away. If necessary, take a Positive Negative Invalid photo of the contents and packaging.

How to Store Biozek COVID-19 Antigen rapid test.

Store the BIOZEK COVID-19 Antigen Rapid Test Cassette packaged in the sealed pouch and extraction buffer at room temperature or refrigerated (2-30°C). The test and extraction buffer are stable through the expiration date printed on the sealed pouch and buffer label. The test must remain in the sealed pouch until use. DO NOT FREEZE. Do not use the kit beyond the expiration date. Do not use the kit if the package of the test cassette or buffer is damaged.

6. Study Population

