7.2 Material and Methods

The Enrollment population consists of up to 250 (minimum of 30 positive and 30 negative samples) symptomatic patients. Enrollment will take place at the subject's home during scheduled visits to patients appointed for an RT-PCR test, as the standard of care procedure, performed by a medical staff member. Medical staff members will perform the RT-PCR test and the samples will be sent to A2Z Diagnostics Laboratory. The results will be available in 1-3 days. Results including Ct and/or FAM values of the RT-PCR test from subjects enrolled to the study will be collected by study personnel.

After completion of the RT-PCR Test, the patients will be asked if they are willing to participate in the BIOZEK Study. If the subject is age 18 or older and meets the inclusion and exclusion criteria, they will sign an Informed Consent Form and will be enrolled into the BIOZEK study. A study personnel will collect demographics information from the subjects; in addition, they will take the subject's body's surface temperature and capture it in the CRF.

Subject will perform 2 additional tests performed in a manner described below:

1. BIOZEK COVID-19 Antigen Rapid Test Cassette-Nasopharyngeal Swab (via self-collection - nasopharyngeal swab sample),

Nasopharyngeal samples will be collected via self-collection and the test will be performed by the subject. The participants will follow instructions for use provided by Biozek included with the test. The subject's performance during self-collection and test performance will be monitored and recorded in a performance form. Results in 15 minutes.

2. BIOZEK COVID-19 Antigen Rapid Test Cassette-Oral Fluid (via self-collection - oral fluid sample)

Oral fluid sample will be collected via self-collection and the test will be performed by the subject. The participants will follow instructions for use provided by Biozek included with the

test. The subject's performance during self-collection and test performance will be monitored and recorded in a performance form. Results in 15 minutes

Test Results

After interpreting the results, the coordinator will take an image of the cassette to be recorded and captured in the CRF. Compliant to all procedures required for disposal of biohazardous waste.

Results will be retrieved from the PCR test when available and all three samples will be analyzed and compared.

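### The objective is the accuracy of a self-performed test, but the plan does not say that the subject's own reading of the cassette is recorded or that it is the result compared with RT-PCR

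*Combined protocol and SAP*

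**What the plan says.** The synopsis and section 4 set the first objective as sensitivity and specificity on a "self-collected sample and self-performed test by subject", for both swab and oral fluid. The introduction gives the intended setting: "The Biozek Antigen Rapid Test can be easily performed by untrained personnel". The end points listed in the synopsis are narrower in wording. They refer to self-collected samples and do not say who performs or reads the test.

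On recording, section 7.2 names two things. A performance form documents how the subject carries out collection and testing. For the result itself there is one sentence: "After interpreting the results, the coordinator will take an image of the cassette to be recorded and captured in the CRF".

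On comparison, the Efficacy Criteria in the synopsis say that "the result of each test performed by the subject will be compared to the RT-PCR test result". Section 8 says that Biozek results will be compared with RT-PCR and that sensitivity and specificity will be calculated. It names no reader.

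The kit text in section 5 includes a reading step for each test. Oral fluid Step 10 speaks to the user: "You have tested positive for COVID-19 antigens, so please contact your doctor". The swab section sets a reading time of 15 minutes, a limit ("Do not interpret the result after 20 minutes") and a colour rule ("Any shade of red color in the test region (T) should be considered positive").

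**The concern.** A visually read cassette has no result until someone reads it, so the reader is part of what is being measured. If the subject does everything except the reading, the trial estimates the accuracy of a self-collected, staff-read test. That is a different quantity from the one in the objective, and less relevant to use by untrained people at home.

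The loss could be permanent. A photograph shows the cassette, not what the subject concluded from it. If the subject's reading is not written down at the time, or is written after the coordinator has commented, no later analysis can restore it. The second objective, the subject's ability to conduct the test, would lose its most direct evidence as well.

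**Working it through.** **Who reads, and whose reading is analysed.** The plan gives no figure on this point, so there is nothing to reproduce. The check is to set the relevant places side by side.

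| Place | Who performs | Who reads | Reading recorded? | Value analysed? |
|---|---|---|---|---|
| Synopsis and section 4, objective | Subject | Not stated | Not stated | Not stated |
| Synopsis, Efficacy Criteria | Subject | Not stated | Not stated | Result of the test the subject performed |
| Synopsis, End Points | Not stated (sample is self-collected) | Not stated | Not stated | Not stated |
| Section 5, oral fluid Step 10 | User | User, by its wording | Not stated | Not applicable |
| Section 7.2, test descriptions | Subject, following the kit instructions | Implied at most | Performance form; no result field mentioned | Not stated |
| Section 7.2, Test Results | Not stated | Coordinator, if read grammatically | Cassette image in the CRF | Not stated |
| Section 8 | Not stated | Not stated | Not stated | Biozek result, reader not named |

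No row says that the subject's reading is written down, that it comes before any staff reading, or which reading counts if the two differ.

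**What a change of reader could do.** The documents give no disagreement rate, so the counts below are assumptions. Among n RT-PCR-positive subjects, let b cassettes be positive to the coordinator only and c be positive to the subject only. Then:

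- coordinator-read minus subject-read sensitivity = (b − c)/n.

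Among RT-PCR negatives the same expression applies to specificity with the sign reversed. A reader who calls more faint lines positive can therefore raise sensitivity and lower specificity. If b = c, the shift is zero.

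Section 6.3 gives a minimum of 30 positive and 30 negative results and a cap of 250 subjects. It does not say that the 30 are counted by RT-PCR, so using 30 as the denominator is a further assumption. The values 60 and 100 are arbitrary points to show the range. The value 220 is 250 − 30, the negatives if 250 enrol with 30 positives.

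| n | One net discordant reading | Two net discordant readings |
|---|---|---|
| 30 | 1/30 = 3.3 points | 2/30 = 6.7 points |
| 60 | 1/60 = 1.7 points | 2/60 = 3.3 points |
| 100 | 1/100 = 1.0 point | 2/100 = 2.0 points |
| 220 | 1/220 = 0.5 points | 2/220 = 0.9 points |

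**What recording both readings would show.** If no disagreement is seen in N cassettes of one test, the two-sided 95% Clopper-Pearson upper limit on the disagreement rate is 1 − 0.025^(1/N). For N = 60 this is 6.0%; for N = 250 it is 1.5%.

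**The case against.** Read as a whole, the protocol leans towards the subject as reader. The subject performs the test and follows kit instructions that include a reading step, Step 10 is addressed to the user, and the Efficacy Criteria tie the compared result to the test the subject performed. The opening phrase of the section 7.2 sentence may only fix when the image is taken. The CRF and performance form may already hold the subject's reading. The shifts shown rest on assumed counts, and at the minimum size they are small beside sampling error: with 27 of 30 positive, the exact 95% interval runs from 73.5% to 97.9%.

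Much of this stands. A reader might infer that the coordinator's reading is the one to be analysed; the documents do not support that, because the sentence is ambiguous and the analysis section is silent. Nor do they support a claim that accuracy would be overstated, since the direction is unknown. The colour rule should not be carried over to oral fluid: it is stated only for the swab test, and it sets a threshold that narrows judgement without removing it.

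The objection does not close the gap. Naming who performed the test does not name who read it, and a field on an unseen form would not tell the analyst which reading to use. Sampling error is no answer either: a confidence interval describes uncertainty about whichever quantity was measured and does not turn a staff-read estimate into a self-read one.

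**Conclusion.** The concern holds as an ambiguity with a real consequence. The objective calls for accuracy in the subject's hands, and the plan neither secures the subject's reading nor makes it the analysed value. Followed literally, it could yield staff-read accuracy under a self-use objective, with the subject's reading lost unless the unseen forms capture it.

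Size and direction cannot be determined from the documents. With 30 assumed to be the number of RT-PCR positives, each net discordant reading is worth 3.3 points of sensitivity; the effect shrinks with larger numbers and vanishes if disagreements balance.

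Two further inferences should be avoided. The mismatch is with the stated objective, not with the listed end points, which require only self-collection. And this is not a problem of knowing the reference result when the cassette is read: section 7.2 says of RT-PCR, "The results will be available in 1-3 days". The issue is who reads the cassette.

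**What to change.** (a) In section 7.2, state that the subject reads each cassette at the kit's stated reading time and records the result before the coordinator looks or comments. The coordinator then makes a separate reading and takes the image, for the swab test within the kit's own reading limit.

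(b) In section 8, state that the subject's recorded reading is the value used for sensitivity and specificity. The coordinator's reading and the image are used only to report subject-coordinator agreement, with a 95% confidence interval for each test.

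The cost is one or two CRF fields if they are not already present, a small extra step at each reading, and one descriptive table. Staff already monitor the tests, and the coordinator already photographs the cassettes. Sample size and eligibility are unaffected. The sponsor should accept that the reported accuracy may differ from a staff-read figure in either direction.

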7.3 Premature Discontinuation

Patients may be withdrawn from the study for the following reasons:

- at patient's own request or at the request of their legally authorized representative
- if, in the opinion of the Investigators, continuation in the study would be detrimental to the subject's well-being
- at the specific request of the Sponsor.

Patients must be withdrawn from the study under the following circumstances:

- intolerable sample collection procedure
- any event that in the judgment of the Investigators poses an unacceptable safety risk to the patient
- study closure

In all cases, the reason for withdrawal must be recorded in the CRF and in the patient's medical records.

7.4 Protocol Violations

Protocol violations include any deviations from this protocol, regardless of prior approval of the violation. A major protocol violation would include the following:

- enrollment of a patient who does not meet the inclusion/exclusion criteria
- enrollment of a patient who has not signed an informed consent form
- the patient has missed the sample collection visit(s)

Any protocol violation must be reported immediately to the Sponsor and to the IRB.

7.5 Compliance

This study will be conducted in accordance with ICH-Good Clinical Practice guidelines.

7.6 Risks

During self-collection the subject will be closely monitored according to standard of care and any adverse effects will be documented.

8. Data analysis

The data will be collected and analyzed by Quality Research and Invention team. Results of RT-PCR, BIOZEK COVID-19 Antigen Rapid Test on self-collected nasopharyngeal sample and BIOZEK COVID-19 Antigen Rapid Test on self-collected oral fluid samples will be analyzed.

Additionally, Ct and/or FAM values for RT-PCR will be obtained.

RT-PCR is a golden standard in diagnosis of COVID-19. The results obtained by Biozek tests will be compared to results of RT-PCR test.

Sensitivity and specificity will be calculated.

9. Ethics

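### Does the plan need a stated endpoint for subject performance, and a rule for counting invalid or repeated self-tests?

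*Combined protocol and SAP*

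**What the plan says.** The synopsis and section 4 give two objectives. The first is the sensitivity and specificity of each cassette. The second is the subject's "performance to collect samples and conduct BIOZEK COVID-19 Antigen Rapid Test". The End Points in the synopsis cover only the first: "Sensitivity and Specificity of BIOZEK COVID-19 Antigen Rapid Test on self-collected nasopharyngeal sample", and the same for oral fluid. The Efficacy Criteria add: "Additionally, the result of each test performed by the subject will be compared to the RT-PCR test result". Section 8 describes a comparison with RT-PCR and ends: "Sensitivity and specificity will be calculated".

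For the second objective, section 7.2 says of each cassette that the subject's "performance during self-collection and test performance will be monitored and recorded in a performance form". It also says: "The participants will follow instructions for use provided by Biozek included with the test".

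Section 5 reproduces kit steps. On the swab side: "If the swab stick breaks during specimen collection, repeat specimen collection with a new swab", and "Do not interpret the result after 20 minutes". A swab test without a control line is to be repeated on a new cassette. An oral fluid test that is invalid is to be referred to the supplier. Section 6.3 sets a maximum of 250 subjects and a minimum of 30 positive and 30 negative results.

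**The concern.** One of two objectives seems to end without a result: data are collected for it, but no measure, denominator or summary is named. That matters because the introduction says untrained people can easily run the test, and objective 2 is the part of the study that would examine this.

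The second worry is the denominator for accuracy. An invalid test is neither positive nor negative, and a repeat gives a second result for the same subject. The swab instructions call for a repeat, while the oral fluid instructions neither state nor forbid one. Only the swab instructions set a latest reading time. With no counting rule in section 8, the choice might be made after the results are known, in an open-label study, and might differ between the cassettes.

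**Working it through.** **1. Objective 2, from aim to result.** The aim is stated (section 4) and the data capture is stated (a performance form per cassette, section 7.2). The endpoint and summary are not. What is missing is a line saying that the form will be tabulated. Data capture is in place, although the form's items are not in the documents.

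The planned size supports such a tabulation. The exact (Clopper-Pearson) 95% limits for x failures in n attempts are the 0.025 quantile of Beta(x, n − x + 1) and the 0.975 quantile of Beta(x + 1, n − x). The failure counts below are assumed. The figure n = 60 takes the 30 + 30 results of section 6.3 as distinct subjects.

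| Failures / attempts | Rate | 95% limits |
|---|---|---|
| 0/60 | 0% | 0 to 6.0% |
| 3/60 | 5.0% | 1.0 to 13.9% |
| 0/250 | 0% | 0 to 1.5% |
| 12/250 | 4.8% | 2.5 to 8.2% |

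Section 6.2 excludes people who cannot self-collect either sample, so any such rate applies to people judged capable.

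**2. The kit instructions side by side.**

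| Event | Swab | Oral fluid | Conflict? |
|---|---|---|---|
| Reading time | 15 minutes, not after 20 | 15 minutes, no latest time in the text shown | No: same nominal time, one text silent on the limit |
| No valid result | Repeat; contact distributor if it persists | Contact supplier for instructions | No: a repeat is not ruled out |
| Swab breaks at collection | Collect again | Not applicable | No: it precedes any test, so there is no second result |

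These are two products, each with its own package insert, and section 7.2 sends subjects to those instructions. The steps in section 5 are shown without their figures. The Efficacy Criteria calculate accuracy separately for each cassette, so the two kits need not share a rule. A late-read swab is already covered, because the instructions bar its interpretation.

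**3. How far the counting rule could move sensitivity.** The plan gives no figure to reproduce. Inputs: 30 positives (section 6.3, taken here as RT-PCR positives) and three assumptions. About 80% of valid first tests are positive; k of the 30 first tests are invalid; under rule C every repeat is positive, which is the upper bound. Let x be 0.8 × (30 − k), rounded.

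- Rule A, invalid tests left out: x / (30 − k)
- Rule B, invalid scored as a missed infection: x / 30
- Rule C, repeats accepted: (x + k) / 30

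| k | A | B | C | C − A |
|---|---|---|---|---|
| 0 | 24/30 = 80.0% (61.4–92.3) | 80.0% | 80.0% | 0 |
| 1 | 23/29 = 79.3% (60.3–92.0) | 23/30 = 76.7% | 24/30 = 80.0% | 0.7 |
| 2 | 22/28 = 78.6% (59.0–91.7) | 22/30 = 73.3% | 24/30 = 80.0% | 1.4 |
| 3 | 22/27 = 81.5% (61.9–93.7) | 22/30 = 73.3% | 25/30 = 83.3% | 1.9 |
| 5 | 20/25 = 80.0% (59.3–93.2) | 20/30 = 66.7% | 25/30 = 83.3% | 3.3 |

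If instead every repeat were negative, accepting repeats would give the figures under B. If repeats are as sensitive as first tests, accepting them leaves the expected estimate where A puts it: at k = 3, (22 + 3 × 22/27) / 30 = 24.44 / 30 = 81.5%. The distance from the k = 3 estimate to its lower limit is 81.5 − 61.9 = 19.6 points.

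**4. The larger drop answers another question.** If a failed first attempt counts as not correct, sensitivity falls by (valid-result sensitivity) × (failure rate). With assumed values of 88.9% (24/27) and 5%, that is 0.889 × 0.05 = 4.4 points. Failure rates of 2% and 10% give 1.8 and 8.9 points. This is the difference between accuracy on valid results and the chance that a first attempt succeeds and is right. It does not measure an error in the planned estimate.

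**The case for a change.** The strongest case for a change is that recording is not analysis. An objective should have a stated result, and a counting rule settled after the data are seen leaves room for choice. At k = 3 the three rules run from 73.3% to 83.3%, and at k = 5 from 66.7% to 83.3%. Attempt number or reading time may also be lost if the form has no field for them.

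Part of this stands. The plan names no summary for objective 2 and no rule for an invalid or repeated test, and a line on each would make it tidier. The wide range, however, comes from scoring an invalid test as negative or from all repeats going one way. Section 5 treats invalid as a result of its own, distinct from negative, so the natural reading keeps it out of the two-by-two table and reports it as a count. Under section 7.2 the RT-PCR result comes back 1 to 3 days later, so a repeat done at the visit is decided without it. Subjects are watched throughout and the coordinator photographs the cassette, so an invalid or repeated test is unlikely to go unseen. Whether the form has every useful field cannot be judged, because its items are not in the documents.

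**Conclusion.** No change to the plan follows. Objective 2 has its data but no named summary, and section 8 is silent on invalid and repeated tests. Both are gaps that a competent analyst fills in the ordinary way: tabulate the performance form per cassette, report the invalid and repeated tests, and calculate accuracy on valid results. The instructions for the two kits are not in conflict. Matching rules across two separately analyzed products, or scoring failed attempts as incorrect, would be a preference.

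The size of any effect is unknown because the documents give no invalid rate. Under the assumptions above, leaving invalid tests out differs from accepting repeats that are all positive by 0.7 to 3.3 points for 1 to 5 invalid tests among 30. The two agree on average if repeats are as sensitive as first tests. Sampling error at 30 positives is around 20 points on the lower side. The conclusion rests on invalid results being reported and not recoded as negative. It would weaken if invalid tests proved common.
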